5.3.1.1 DXA

DXA is recognized as the reference method to measure BMD as well as soft-tissue composition (body composition: lean mass, fat mass) with acceptable accuracy errors and good precision and reproducibility. Subjects with a centrally read screening DXA T-score (total spine, total hip or femoral neck) greater than a -2.5 S.D. will be enrolled and randomized for treatment. Adequacy of DXA scans should also be confirmed by the central imaging lab prior to randomization.

Screening results to confirm eligibility (DXA T-score) will be returned to the site by the central imaging lab. No other results will be provided to the site.

Bone imaging (hip and lumbar spine) will be performed at all imaging facilities and body composition (whole body), an exploratory measure, will be additionally carried out at imaging facilities with the appropriate hardware/software.

DXA will be conducted at baseline, end of treatment (Day 112, +/- 1 week) and approximately 6 months after the end of the treatment (Day 292, +/- 2 weeks).

Screening DXA should be performed approximately 21 days prior to the Day 1 dose. Eligibility should be confirmed by central imaging lab prior to entry into the lead-in period (Day -7).

A repeat DXA may be performed if clinically indicated.

Imaging assessments will be performed at time points indicated in [Table 5.1-1](#), [Table 5.1-2](#) and [Table 5.1-3](#).

5.3.2 Laboratory Test Assessments

A central/local laboratory will perform the analyses and will provide reference ranges for these tests. Results of clinical laboratory tests performed prior to Day 1 must be available prior to dosing.

The following clinical laboratory tests will be performed:

Hematology

Hemoglobin
Hematocrit
Total leukocyte count, including differential
Platelet count

Serum Chemistry

Aspartate aminotransferase (AST)	Total Protein
Alanine aminotransferase (ALT)	Albumin
Total bilirubin	Sodium
Direct bilirubin	Potassium

Alkaline phosphatase	Chloride
Lactate dehydrogenase (LDH)	Calcium
Gamma-glutamyl transferase (GGT)	Phosphorus
Creatinine	Magnesium
Blood Urea Nitrogen (BUN)	Creatine kinase
Uric acid	Creatine Clearance (CICr) - at Screening only
Fasting glucose	calculated using Modification of Diet in
	Renal Disease (MDRD) equation.

Urinalysis

Protein
Glucose
Blood
Leukocyte esterase
Specific gravity
pH
Microscopic examination of the sediment if blood, protein or leukocytes esterase are positive on the dipstick

Serology

Serum for hepatitis C antibody, hepatitis B surface antigen (screening only)

Other Analyses

INR (per [Table 5.1-1](#), [Table 5.1-2](#) and [Table 5.1-3](#))
HbA1c (Screening, and per [Table 5.5.1-1](#))
AFP (Screening - for inclusion/exclusion)
FSH (Screening only; females)
Lipid panel (triglycerides, total cholesterol, LDL and HDL at Screening and per [Table 5.5.1-1](#))
Pregnancy test (WOCBP only: per [Table 5.1-1](#), [Table 5.1-2](#) and [Table 5.1-3](#))

Results of all laboratory tests required by this protocol must be provided to BMS, either recorded on the laboratory pages of the CRF or by another mechanism as agreed upon between the investigator and BMS (e.g., provided electronically). If the units of a test result differ from those printed on the CRF, the recorded laboratory values must specify the correct units. Any abnormal laboratory test result considered clinically significant by the investigator must be recorded on the appropriate AE page of the CRF (see [Section 6.3](#) Laboratory Test Result Abnormalities).

5.3.3 Monitoring of Injection site reactions

Injection site reactions will be monitored from Day -7 through the end of the out-patient follow-up period. The Draize Scale for erythema and edema will be used as a guide for reporting AEs at the blinded study drug injection site, see [Table 5.3.3-1](#).

Table 5.3.3-1: Monitoring of injection site reactions

Erythema		Edema	
Description	AE Grade	Description	AE Grade
No erythema	-	No edema	-
Very slight erythema (barely perceptible)	Mild	Very slight edema (barely perceptible)	Mild
Well defined erythema	Mild	Well defined edema	Mild
Moderate erythema	Moderate	Moderate edema (raised approx. 1 mm)	Moderate
Severe erythema (beet redness to slight eschar formation)	Severe	Severe edema (raised more than 1 mm and beyond exposure area)	Severe

5.4 Efficacy Assessments

5.4.1 Efficacy Imaging Assessment for the Study

Image acquisition guidelines and submission processes will be outlined in the MB130045 Imaging Manual, to be provided by the central imaging lab. A central imaging lab will perform all imaging analyses. The clinical site will be trained in imaging procedures prior to scanning the first study subject. Images will be submitted to the central imaging lab for central review. The site will be informed of quality issues or needs for repeat scanning via queries from the central imaging lab.

Any incidental findings of potential clinical relevance that are not directly associated with the objectives of the protocol should be evaluated and handled by the Study Investigator as per standard medical/clinical judgment.

5.4.1.1 MRI

Proton density hepatic fat-fraction MRI will be employed at screening phase to determine hepatic fat fraction (%). Subjects with a centrally read hepatic fat fraction $\geq 10\%$ at screening will be enrolled and randomized for treatment. Adequacy of MRI should also be confirmed by the central imaging lab prior to randomization.

Screening results to confirm eligibility (hepatic fat fraction) will be returned to the site by the central imaging lab. No other results will be provided to the site.

MRI will be conducted during the screening period, Day 57 (+/- 1 week), and at the end of treatment visit (Day 112, +/- 1 week), or if applicable, at the early termination visit (conducted only if subject received ≥ 6 weeks of study drug and was ≥ 1 month from previous MRI).

Screening MRI should be performed approximately 21 days prior to the Day 1 dose. Eligibility should be confirmed by central imaging lab prior to entry into the lead-in period (Day -7). A repeat MRI may be performed if clinically indicated.

Imaging assessments will be performed at time points indicated in [Table 5.1-1](#), [Table 5.1-2](#) and [Table 5.1-3](#).

5.5 Pharmacokinetic Assessments

The following pharmacokinetic parameters of BMS-986036 (Total and C-Terminal intact) will be generated and summarized

Ctrough Observed serum concentration before the next dose is administered; the pre-dose concentration

5.5.1 *Pharmacokinetics and Pharmacodynamics: Collection and Processing*

[Table 5.5.1-1](#) lists the sampling schedule to be followed for the assessment of pharmacokinetics and pharmacodynamics. Further details of blood and urine collection and processing will be provided to the site in the procedure manual.

Table 5.5.1-1: Pharmacokinetic and Pharmacodynamic Sampling Schedule for BMS-986036

Study Day	Event	Time (Relative To BMS-986036 Dose) Hour: Min	BMS-986036 (a) PEG-C-Term-Intact (b) PEG-Total (c) Endogenous FGF21	Immunogenicity		^a Fasting lipids		^c NASH FibroSure				Additional Research
1	Predose	0:00	X	X		X		X				X
15	Predose	0:00	X	X								
29	Predose	0:00	X	X		X						
43	Predose	0:00	X									
57	Predose	0:00	X	X		X						
57		6:00	X									
86	Predose	0:00	X	X		X						
112	Predose	0:00	X	X		X		X				
142	Follow-up		X ^h	X		X						
Approximately every 6-8 weeks between D142 or	Immunogenicity Follow-Up		X ^{h,i}	X ⁱ								

Table 5.5.1-1: Pharmacokinetic and Pharmacodynamic Sampling Schedule for BMS-986036

Study Day	Event	Time (Relative To BMS-986036 Dose) Hour: Min	BMS-986036 (a) PEG-C-Term-Intact (b) PEG-Total (c) Endogenous FGF21	Immunogenicity		^a Fasting lipids		^c NASH FibroSure		Additional Research
D292 and up to 12 months after D142										
292	Follow-up		X ^h	X						
Early Term Visit on treatment	Early Term		X	X		X		X		
Early Term visit (post treatment prior to Day 142)	Early Term		X ^{h,i}	X ⁱ		X				

^a Lipids include triglycerides, total cholesterol, LDL and HDL

^b Residual samples will analysis of be banked for further biomarkers defined in the section.

^c NASH FibroSure includes measurement for α2-macroglobulin, ApoA1, haptoglobin, gamma-glutamyl transpeptidase (GGT), bilirubin; fasting glucose, triglycerides, cholesterol, ALT, AST, age and BMI.

^d Bone biomarkers: BSAP, P1NP, CTX.

█ [REDACTED]
█ [REDACTED]
█ [REDACTED]

h Only Endogenous FGF21 to be collected.

i Only applies to subjects with positive immunogenicity at D142 and/or D292. Immunogenicity follow-up visits will commence after D142 or D292, if immunogenicity results are positive at D142 or D292, respectively, without evidence of decreasing or stable antibodies. Assessments may continue, approximately every 6-8 weeks, for up to 12 months following the Day 142 visit and will be discontinued when antibodies have resolved or are judged by the Medical Monitor to be decreasing or stable.

[REDACTED]

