All subjects will be monitored for occurrence of ADA and anti-FGF21 antibodies during dosing, at approximately 4 weeks following the last dose (D142 follow-up visit), and at approximately 6 months following the last dose (D292 follow-up visit). If present, antibodies will be assessed for neutralizing activity. Subjects with a positive result in the ADA and/or anti-FGF21 antibody assays at the Day 142 or Day 292 follow-up visits, without evidence of decreasing or stable antibodies, will be followed afterwards with immunogenicity assessments for up to 12 months after the D142 visit until antibody levels resolve or demonstrate a consistent decreasing trend. These immunogenicity follow-up visits will be conducted approximately every 6-8 weeks.

In addition, endogenous FGF21 will be measured at all follow up visits, including the D142 and D292 follow up visits and the immunogenicity follow up visits (for subjects with positive ADA and/or anti-FGF21 antibodies at D142 and/or D292, without evidence of decreasing or stable antibodies).

Bone effects

No bone resorption marker change has been observed in subjects in the first in human study (MB130001). Bone formation markers were slightly reduced in all subjects in the MAD, including those treated with placebo, and only in subjects treated with the highest daily dose (30 mg daily) were bone markers reduced to an extent greater than placebo. A BMS-986036-related bone risk to adult humans is considered low; unlike thiazolidinediones (TZDs), bone resorption markers were not increased. To minimize the potential risk to subjects in whom a reduction of bone formation markers could impact skeletal healing, those with recent fracture or orthopedic surgery will be excluded.

To assess whether chronic dosing of BMS-986036 has the potential to modulate bone turnover and vitamin D and mineral metabolism, bone turnover markers (BSAP, P1NP and CTX-1), PTH and 1,25 dihydroxy vitamin D along with calcium, magnesium, phosphorus are being assessed in the ongoing MB130002 study in T2DM subjects. .

In this study, we will continue to monitor bone turnover markers, calcium, magnesium and phosphorus before and after the dosing period. Samples for PTH and 1,25 dihydroxy vitamin D will be collected, and may be assayed if a perturbation is observed in the MB130002 study.

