Patient diary review	X	X	X	X	X	X	X	X	
^a Early Termination is not a scheduled visit. For early termination PK and PD assessments, refer to Table 5.5.1-1 Abbreviations: D = Day									

Table 5.1-3: Post Treatment Follow-up Procedural Outline (MB130045)

Procedure	D 142 (30 days after last dose)	D 292 (6 mo after last dose)	Follow-up for immunogenicity ^a (up to 12 months post Day 142)	Early Termination Visit ^b	Notes
Visit Window	+/- 3 days	+/-2 wk	n/a		
IVRS Call	X			X	
Safety Assessments					
Physical Examination	X			X	
Targeted Physical Examination					Injection site reactions (as measured by the Draize Scale for erythema and edema (see Section 5.3.3), others as clinically indicated. See note in Screening procedures.
Physical Measurements	X			X	Weight (using calibrated scale), BMI and waist circumference measurement.
Vital Signs	X			X	See note in screening procedures.
Electrocardiograms (ECGs)	X			X	See note in screening procedures.
Laboratory Tests (hematology, clinical chemistry, urinalysis, INR)	X			X	See note in screening procedures.
Pregnancy Testing	X			X	Female subjects of child-bearing potential. Urine pregnancy testing to be performed at post treatment specified visits with reflex to serum if urine pregnancy testing is positive.
Dual-emission X-ray Absorptiometry (DXA)		X			Bone imaging (hip and lumbar spine) at all imaging facilities.
Adverse Event Reporting					
Monitor for Adverse Events	X			X	Up to 30 days after the last dose.
Monitor for Serious Adverse Events	X			X	See note in screening procedures.
Pharmacokinetic (PK) Assessments					
PK Sampling	X	X			Refer to Table 5.5.1-1
Immunogenicity testing	X	X	X	X	Refer to Table 5.5.1-1 and Section 5.7
████████████████████	██████████				
██████████	██████████				

^a Applies only to subjects with positive immunogenicity at D142 and/or D292. (Refer to [Section 5.7](#)). These immunogenicity follow-up visits will commence after D142 or D292, if immunogenicity results are positive at D142 or D292, respectively, without evidence of decreasing or stable antibodies.

^b Early Termination is not a scheduled visit. For early termination PK and PD assessments, refer to [Table 5.5.1-1](#)

Abbreviations: D = Day

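### Table 5.5.1-1 ties the antibody and endogenous FGF21 samples at post-treatment early termination to a Day 142 or Day 292 result that cannot yet exist, contradicting Table 5.1-3 and Section 1.5.1

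*Protocol*

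**What the plan says.** Protocol Table 5.5.1-1 (Section 5.5.1) has two early-termination rows. The one labelled "Early Term Visit on treatment" has plain marks for the drug/FGF21 sample and for immunogenicity. The other begins "Early Term visit (post treatment prior to Day 142"; its drug/FGF21 mark carries footnotes h and i, and its immunogenicity mark carries footnote i. Footnote h says "Only Endogenous FGF21 to be collected". Footnote i says "Only applies to subjects with positive immunogenicity at D142 and/or D292".

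Protocol Table 5.1-3 (Section 5.1) marks immunogenicity testing at Day 142, at Day 292, at the repeat immunogenicity follow-up and at the Early Termination Visit. Its positivity limit, footnote a ("Applies only to subjects with positive immunogenicity at D142 and/or D292"), is attached to the repeat follow-up column only. The note on the immunogenicity row is "Refer to Table 5.5.1-1 and Section 5.7", and the early-termination footnote is "Early Termination is not a scheduled visit. For early termination PK and PD assessments, refer to" Table 5.5.1-1. The PK sampling row is blank at early termination.

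Protocol Section 1.5.1 states the intent: "All subjects will be monitored for occurrence of ADA and anti-FGF21 antibodies during dosing, at approximately 4 weeks following the last dose", and again about 6 months after it. The same section says endogenous FGF21 is measured at every follow-up visit.

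Protocol Section 8.3.2 and SAP Section 4.4 define the secondary immunogenicity endpoint by the time points in Table 5.5.1-1.

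**The concern.** A condition that no subject can satisfy cancels the marks it is attached to. Read as written, Table 5.5.1-1 schedules two samples and then makes both impossible to trigger. The other places that deal with antibody sampling after treatment point the other way.

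Immunogenicity is a secondary objective. Section 1.5.1 also treats it as a named risk, including the theoretical possibility of neutralizing antibodies that cross-react with endogenous FGF21. For a subject who leaves the study after the last dose and before Day 142, the early-termination visit is the last planned opportunity to test for antibodies. If the site follows Table 5.5.1-1, that opportunity is lost. Some sites may follow one table and some the other, so collection could also differ between sites with no rule to explain it.

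**Working it through.** The plan gives no figure on this point, and none is needed. The check compares the rows and tests whether footnote i can be satisfied in each.

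**Timing.** Treatment ends at Day 112 and the first follow-up visit is Day 142, so the row covers the 142 − 112 = 30 days between them. Table 5.1-3 gives Day 142 a window of 3 days either side, so the earliest qualifying result is at about Day 139 (142 − 3), and a sample taken then would be the Day 142 sample itself. At a termination visit before that, neither a Day 142 nor a Day 292 result exists. The set of subjects who meet footnote i is empty.

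**Marks in Table 5.5.1-1.**

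| Row | Drug/FGF21 mark | Antibody mark | Can footnote i be met? |
|---|---|---|---|
| Early termination on treatment | plain | plain | not applied |
| Day 142 | h | plain | not applied |
| Repeat follow-up, every 6–8 weeks | h and i | i | yes |
| Day 292 | h | plain | not applied |
| Early termination after treatment, before Day 142 | h and i | i | never |

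Footnote i makes sense on the repeat follow-up row, which exists only for subjects already found positive. The last row carries the same pair of superscripts, which suggests they were carried over. Fasting lipids in that last row have no footnote, so the visit is meant to take place and blood is meant to be drawn at it.

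**Against Table 5.1-3, antibodies.** That table marks the sample at early termination and keeps the positivity limit on the repeat follow-up column. This is a direct contradiction. Table 5.1-3 does not resolve it, because its note sends the reader back to Table 5.5.1-1.

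**Against Table 5.1-3, endogenous FGF21.** The PK sampling row is marked at Days 142 and 292, where footnote h allows only endogenous FGF21. So in the follow-up table a mark in that row stands for the endogenous FGF21 sample, and the blank at early termination means it is not scheduled there. For this analyte neither table yields a sample, and the conflict is with Section 1.5.1.

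**Who is affected.** Sections 3.5 and 3.6.1 keep subjects who only stop study drug in protocol follow-up, so they still reach Days 142 and 292. Subjects who terminate while on treatment fall under the unfootnoted row. That leaves subjects who leave the study between the last dose and Day 142 and still attend a termination visit.

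**The case against.** The strongest objection is that this is a misplaced footnote whose intended meaning is plain elsewhere. Table 5.1-3 marks the antibody sample, Section 1.5.1 speaks of all subjects, and Section 5.9.3 lets the investigator take an unscheduled immunogenicity sample. A sensible site might simply draw the blood. The group is narrow and the primary endpoint is not involved.

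Much of that stands, and it limits what can be claimed. A reader might infer any of the following, and the documents do not support them:

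- **That these subjects get no antibody sample after stopping drug.** This would follow only if footnote i overrode everything else. Table 5.1-3 and Section 1.5.1 say otherwise, so the supportable statement is that the sample is not due under Table 5.5.1-1 and may be omitted.
- **That the 10% allowance in Protocol Section 8.1 gives the number affected.** That allowance is for subjects without post-baseline assessments for the MRI comparison. The last scheduled MRI is at Day 112, so someone who finishes treatment and then leaves would normally not be in it.
- **That a known share of antibody positives would be missed.** The first-in-human rate (3 of 72) says nothing about how many subjects leave in this window, and positives found at earlier on-treatment samples would already be counted.
- **That circulating drug hides antibodies in the on-treatment samples.** Section 5.7 gives drug-tolerance limits for the ADA assay, but the available text gives no serum concentrations to set against them, and the anti-FGF21 assay's tolerance is above 48 µg/mL at every antibody level tested. A visit soon after the last dose may not be drug-free either, since Section 3.3.1 equates five half-lives with 30 days.

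Section 1.5.1 also does not name the early-termination visit, so the conflict with it rests on its wording for all subjects and all follow-up visits.

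The objection does not remove the contradiction. The table with the faulty condition is the one the other table defers to and the one that defines the endpoint's time points. Sampling under Section 5.9.3 is discretionary.

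**Conclusion.** The point holds as an internal contradiction with a practical consequence. Footnote i cannot be satisfied on the row for early termination before Day 142, so Table 5.5.1-1 makes neither the antibody nor the endogenous FGF21 sample due. For antibodies this conflicts with Table 5.1-3 and Section 1.5.1. For endogenous FGF21 it conflicts with Section 1.5.1, and Table 5.1-3 offers no competing mark.

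The consequence is that sites may omit the last planned antibody sample for subjects who leave the study between the last dose and Day 142. The number is not given and is probably small. No effect on the antibody rate can be calculated from the documents. The conclusion assumes that sites treat Table 5.5.1-1 as governing, as the cross-references direct, and that the superscripts are read correctly from the table. Their agreement with the repeat follow-up row, where the same pair makes sense, supports that reading.

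**What to change.** In Table 5.5.1-1, remove footnote i from both marks in the row for early termination after treatment and before Day 142. Keep footnote h there, and keep footnote i on the repeat follow-up row. In Table 5.1-3, add a mark for endogenous FGF21 at the Early Termination Visit, limited to that analyte as at Days 142 and 292. The two tables and Section 1.5.1 then agree. SAP Section 4.4 points to the protocol table and needs no separate edit.

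The cost is a small protocol text change and about one extra tube per affected subject, at a visit where laboratory tests and lipids are already drawn.

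This does not alter when extended antibody follow-up starts. Section 5.7 still ties it to a positive result at Day 142 or Day 292, so a positive result at early termination would be recorded but would not by itself start repeat visits.

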5.7 Immunogenicity

Subjects will be monitored for antibodies to study medication using a validated ADA homogenous bridge assay with BMS-986036 and electrochemical luminescence detection. Samples will first be screened for potential positive ADA responses. Then the samples with positive ADA responses will be confirmed for specificity using an immunodepletion format with drug BMS-986036 and un-PEGylated drug. The reactivity of confirmed positive responses will be characterized as “BMS-986036” (specific to the FGF21 region) or “PEG” (specific to the PEGylated region) based on the immunodepletion specificity. Additionally, samples with confirmed positive responses will be tittered to determine the relative positive response. The sensitivity was determined to be 20 ng/mL and the drug tolerance at antibody concentrations of 50, 100, 500, and 10,000 ng/mL was determined to be 1, 4, 16, and 48µg/mL of BMS-986036 respectively.

Subjects will also be monitored for antibodies to FGF21 using a validated homogenous bridge assay with Met-FGF21 (recombinant produced) and electrochemical luminescence detection. Samples will first be screened for potential positive anti-FGF21 responses. Then the samples with positive anti-FGF21 responses will be confirmed for specificity using an immunodepletion format with wild type sequence FGF21 (WSFGF-21). Samples with confirmed positive anti-FGF21 responses will be titrated to determine the relative positive response. The sensitivity was determined to be ≤ 5 ng/mL and the drug tolerance at antibody concentrations of 50, 100, 500, and 10,000 ng/mL was determined to be > 48 µg/mL of BMS-986036.

Samples positive for ADA or positive for anti-FGF21 antibodies will be tested for neutralizing activity in a validated cell based neutralizing antibody assay. The assay measures the ability of an ADA or anti-FGF21 antibody to inhibit or block Elk1 activation that is induced when FGF21 or drug binds to the β Klotho and FGF receptors. The sensitivity was determined to be 4000 ng/mL and the drug tolerance at antibody concentrations of 400, 16,000 and 32,000 ng/mL was determined to be 0.4, >1.0, and >1.0 μ g/mL of BMS-986036 respectively.

Samples will be banked for additional immunogenicity characterization if needed.

Subjects with positive ADA and /or anti-FGF21 antibody results at the Day 142 visit and/or the Day 292 visit may be asked to return for antibody testing. Immunogenicity follow-up visits will commence after D142 or D292, if immunogenicity results are positive at D142 or D292, respectively, without evidence of decreasing or stable antibodies. Assessments may continue, approximately every 6-8 weeks, for up to 12 months following the Day 142 visit and will be discontinued when antibodies have resolved or are judged by the Medical Monitor to be decreasing or stable.

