3.3.1 Inclusion Criteria

1. Signed Written Informed Consent

- a. Signed informed consent form.

2. Target Population

- a. Liver biopsy performed within 1 year of Screening or may be performed between Screening and Lead-in (Day -7) with documented results of NASH with NASH CRN fibrosis stage 1-3, or equivalent using a different scoring system.
- b. Body mass index (BMI) of ≥ 25 . Note: $BMI = \text{weight (kg)} / [\text{height (m)}]^2$
- c. Hepatic fat fraction (%) $\geq 10\%$ by MRI performed during the Screening period.
- d. Subject is able to medically tolerate the performance of the MRI or DXA scans and has suitable weight and circumference. See [Section 3.4.3](#) for further details.
- e. Subject agrees not to initiate a weight loss program and agrees to maintain consistent dietary habits and exercise regimen for the duration of the study.
- f. Subject re-enrollment: This study permits the re-enrollment of a subject that has discontinued the study as a pre-treatment failure (i.e., subject has not been randomized / has not been treated). If re-enrolled, the subject must be re-consented and will receive a new subject number.

3. Age and Reproductive Status

- a. Males and females, ages 21 to 75 years, inclusive
- b. Women of childbearing potential (WOCBP) must have a negative serum or urine pregnancy test (minimum sensitivity 25 IU/L or equivalent units of HCG) within 24 hours prior to the start of study drug.
- c. Women must not be breastfeeding.

- d. WOCBP must agree to follow instructions for method(s) of contraception for at least 4 weeks before dosing, for the duration of treatment with study drug (s) 16 weeks plus 5 half-lives of study drug (30 days) plus 30 days (duration of ovulatory cycle) for a total of 2 months post-treatment completion.
- e. Males who are sexually active with WOCBP must agree to follow instructions for method(s) of contraception for the duration of treatment with study drug (16 weeks) plus 5 half-lives of the study drug (30 days) plus 90 days (duration of sperm turnover) for a total of 4 months post-treatment completion.
- f. Azoospermic males and WOCBP who are continuously not heterosexually active are exempt from contraceptive requirements. However they must still undergo pregnancy testing as described in this section.

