4.5 Selection and Timing of Dose for Each Subject

At the time of entry into the lead-in period (Day -7 visit), the site will call IVRS in order for the lead-in medication to be assigned and dispensed. Subjects who successfully complete the lead-in period and meet the criteria for entry into the treatment period (see [Section 3.3](#)), will be randomly assigned by the IVRS to one of the following 3 double-blind treatment groups in a 1:1:1 ratio:

- BMS-986036 10 mg once daily (QD)
- BMS-986036 20 mg once weekly (QW)
- Placebo (QD)

Randomization will be stratified based upon diagnosis of Type 2 diabetes mellitus (yes vs. no).

The two strata for randomization are defined as follows:

- Strata 1: Diabetes Mellitus - Yes
- Strata 2: Diabetes Mellitus - No

Randomized subjects who discontinue will not be replaced.

Randomization schedules for both subject treatment and containers will be generated and kept by Bristol- Myers Squibb and stored in a secure location with restricted access.

At all study visits when study medication is dispensed, each subject will be assigned a kit number by the IVRS. Kit numbers will be assigned randomly and will correspond to the numbers printed on the packages and kits containing study drug. Kit numbers will be recorded on the appropriate eCRFs. The IVRS will be available 24 hours per day, 7 days per week.

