8.4.6 Immunogenicity Analyses

Responses of anti-BMS-986036 antibodies and anti-FGF21 antibodies will be listed and tabulated by treatment and study day. The relationship between immunogenicity and PK and/or PD may be explored.

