4.4 Immunogenicity Endpoints

The second secondary objective to assess the effect of daily or weekly doses of BMS-986036 on immunogenicity in NASH subjects will be measured by anti-BMS-986036 antibodies and anti-FGF21 antibodies at the specified time points in Table 5.5.1-1 of the Protocol.

[REDACTED]

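### Circulating drug may hide low-level anti-drug antibody (ADA) in on-treatment samples, more often in the daily arm, while protocol 8.4.6 leaves the link to drug level optional

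*Protocol*

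**What the plan says.** Immunogenicity is a secondary objective (protocol 1.3.2) and a named risk (1.5.1). Protocol 5.7 describes two antibody assays.

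- **ADA assay.** "The sensitivity was determined to be 20 ng/mL". With drug in the sample, the "drug tolerance at antibody concentrations of 50, 100, 500, and 10,000 ng/mL was determined to be 1, 4, 16" and 48 µg/mL. Confirmed positives are typed as directed at the FGF21 region or at the PEG.
- **Anti-FGF21 assay.** "Subjects will also be monitored for antibodies to FGF21 using a validated homogenous bridge assay". Its sensitivity is 5 ng/mL or better and its tolerance is above 48 µg/mL at all four antibody levels. It confirms with wild-type FGF21.

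Table 5.5.1-1 takes ADA samples predose on Days 1, 15, 29, 57, 86 and 112, each with a drug sample, and again at Days 142 and 292. At those two follow-up visits only endogenous FGF21 is measured.

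On analysis, protocol 8.4.6 says: "Responses of anti-BMS-986036 antibodies and anti-FGF21 antibodies will be listed and tabulated by treatment and study day". Its next sentence allows the relation of immunogenicity to PK or PD to be explored but does not commit to it. SAP 4.4 says that the objective "will be measured by anti-BMS-986036 antibodies and anti-FGF21 antibodies at the specified time points in Table 5.5.1-1 of the Protocol". The visible SAP text passes from 7.6.7, through redacted blocks, to 7.10, so its immunogenicity analysis cannot be read.

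**The concern.** A bridging assay can fail to see antibody when enough drug is present. The stated tolerances say when this can happen: above 1 µg/mL of drug for 50 ng/mL of antibody, and above 4 µg/mL for 100 ng/mL. The arms carry different amounts of drug. If a masked sample is tabulated as non-positive, the daily arm could look less immunogenic on treatment than it is. Antibody present during dosing could first appear at Day 142 and be read as late onset. A dip in the weekly arm at Day 86 could also be interference. At stake are on-treatment ADA incidence and onset timing. The primary endpoint is not affected.

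**Working it through.** The tolerances are assay validation results, so no formula reproduces them. The check is whether drug could plausibly exceed them, and in which arm.

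**Inputs from the protocol**
- Doses (4.5): 10 mg daily, which is 7 × 10 = 70 mg per week, against 20 mg weekly. Ratio 3.5.
- Half-life: inclusion criterion 3d (3.3.1) uses "16 weeks plus 5 half-lives of study drug (30 days"), so 30/5 = 6 days. This comes from a contraception rule and may be conservative.
- Timing (3.1, Table 4-1): the weekly active dose falls on Days 1, 8, …, 106. Days 15, 29 and 57 are therefore 7 days after an active dose, Day 112 is 6 days after, and Day 86 is 1 day after.

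**Assumed, because the documents do not give them:** volume V, bioavailability F, one compartment, instant absorption.

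**Formula.** Predose amount in the body = Σ dose × 2^(−days since dose / half-life). Concentration (µg/mL) = amount (mg) × F / V (L).

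**Amounts at a 6-day half-life, near steady state**
- Daily: r = 2^(−1/6) = 0.891; 10 × 0.891/0.109 = 81.7 mg.
- Weekly, 7 days after a dose: s = 2^(−7/6) = 0.445; 20 × 0.445/0.555 = 16.0 mg.
- Weekly, Day 112: 20 × 0.5/0.555 = 18.0 mg.
- Weekly, Day 86: 20 × 0.891/0.555 = 32.1 mg.
- Daily, Day 142: (81.7 + 10)/32 = 2.9 mg.

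At Day 15, before steady state, the amounts are 65 mg (daily) and 13 mg (weekly). No volume is needed to state the condition for masking. The 1 µg/mL tolerance is exceeded if V/F is below 65 to 82 L in the daily arm, or below 13 to 18 L in the weekly arm (32 L at Day 86). The 4 µg/mL tolerance needs V/F below 16 to 20 L (daily), or 3 to 4.5 L (weekly; 8 L at Day 86).

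**Daily-to-weekly ratio at 6 days**, allowing slower absorption (0.7 or 2 per day): 4.4 to 5.1 at Days 15, 29 and 57; 4.1 to 4.5 at Day 112; 2.5 to 3.2 at Day 86. Over half-lives of 1 to 6 days, the Day 86 ratio is 1.0 to 3.2.

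**Scenario counts** (half-life 2, 4, 6 days; V 5, 10, 20 L; F 0.5, 1; 18 in all)

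| Visit | Daily >1 µg/mL | Weekly >1 | Daily >4 | Weekly >4 |
|---|---|---|---|---|
| Days 15, 29 | 17 | 4 | 7 | 0 |
| Day 57 | 17 | 4 | 9 | 0 |
| Day 86 | 17 | 13 | 9 | 2 |
| Day 112 | 17 | 6 | 9 | 0 |
| Day 142 | 0 | 0 | 0 | 0 |

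At Day 57 the daily-arm level runs from 0.6 to 16.3 µg/mL. The 16 µg/mL tolerance (500 ng/mL of antibody) is passed in at most 1 of 18. The highest Day 142 level is 0.57 µg/mL.

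**Sensitivity to the grid.** With half-life 1, 2, 4, 6 days, V 5, 10, 20, 40 L and F 0.3, 0.5, 0.75, 1, the daily arm at Day 57 exceeds 1 µg/mL in 37 of 64 and 4 µg/mL in 13 of 64. At a 1-day half-life on the narrower V and F it is 1 of 6. The counts show what is possible. They are not probabilities.

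**The case against.** **Masking is not demonstrated.** A reader might infer from the tolerance figures that interference does occur. They do not show that. No serum concentration, volume or clearance is given, and the result moves with the assumptions. This stands.

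**The plan does not ignore drug level.** A reader might also infer that it does, or that the SAP lacks a rule. Protocol 8.4.6 permits a PK analysis, and the SAP section is not visible, so neither inference is supported. No visible text defines ADA status categories either, so that a masked sample is counted as negative is itself a reading. What remains is that the protocol's committed output is a table by arm and day.

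**The arm and visit pattern is blurred.** The clinic windows are +3 days at Days 15 to 86. If the weekly dosing day is kept, a Day 57 visit held on Days 58 to 60 falls 1 to 3 days after an active dose, with 32.1 to 25.5 mg in the body rather than 16.0 mg (6-day half-life). This stands too.

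**Much is covered already.** The anti-FGF21 assay would still find antibody that reacts with FGF21. All subjects are due samples at Days 142 and 292, and extended follow-up depends on those visits. No formal between-arm ADA test is planned. At the first-in-human rate in 1.5.1 (3/72 = 4.2%), about 30 × 0.042 = 1.3 positives per arm would be expected, too few to show a clear pattern. These points limit the harm. They do not cover PEG-specific antibody, on-treatment timing, or subjects who miss the follow-up visits.

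**Conclusion.** The point holds as a possibility with limited scope. By the stated tolerances, low-level ADA may go undetected on treatment, more often in the daily arm at Days 15, 29, 57 and 112, with a smaller arm difference at Day 86. Whether it does depends on serum levels that the trial will measure but the documents do not report. The exposure is confined to antibody below about 500 ng/mL that the anti-FGF21 assay does not detect, such as PEG-specific antibody, and to on-treatment incidence and onset timing. Post-treatment status is little affected, because about 3% of the drug (1/32) remains at Day 142 at a 6-day half-life. No omission is claimed for the SAP. The change is worth making because it uses each subject's measured level and so needs none of the assumptions above. If levels prove low, nothing is reclassified.

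**What to change.** In protocol 8.4.6, and in the SAP if it is not already there:

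1. Report each on-treatment non-positive ADA result with its paired predose total BMS-986036 level. Class it as negative or inconclusive against a pre-specified stated tolerance, for example 1 µg/mL (50 ng/mL of antibody), with 4 µg/mL (100 ng/mL) as a second cut. Placebo samples carry no drug and stay conclusive.
2. Show the inconclusive count beside percent positive, by arm and visit.
3. Summarise ADA by arm as ever-positive after baseline, including Days 142 and 292, and show those off-drug visits separately. Using the off-drug visits alone would lose transient responses.
4. State that a rise from Day 112 to Day 142 is not, on its own, to be read as new onset.

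The cost is wording and one merge of PK and ADA data already collected, with no new sample or assay. The downside is that some on-treatment results, mostly in the daily arm, become inconclusive. If daily-arm levels are high, the 1 µg/mL cut could reclassify most of that arm's non-positive results, which is why a second cut is useful.
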